4.2 Other Restrictions

4.2.1 Subject Admission

The subject will be hospitalized between the day before IMP administration in Period 1 and the day after IMP administration in Period 3 (8 nights and 9 days).

4.2.2 Self Care

The subject will be instructed to avoid strenuous exercises, excessive eating and drinking, and irregular hours such as staying up late during participation in the trial.

4.2.3 Restricted Foods

- The table below specifies the food products not allowed to be taken by subjects, together with the applicable periods of restriction.

Food	Restricted period
Any food/beverage containing methylxanthine	During hospitalization
Any food/beverage containing alcohol	Between 3 days before IMP administration in Period 1 and discharge in Period 3
Any food/beverage containing St. John's wort	Between 14 days before IMP administration in Period 1 and discharge in Period 3
Any food/beverage containing grapefruit, Seville orange, or star fruit	Between 7 days before IMP administration in Period 1 and discharge in Period 3
Smoking	Between 60 days before IMP administration in Period 1 and discharge in Period 3

- The subject will be allowed to take only permitted foods/beverages during hospitalization.
- During hospital stay, the subject will have breakfast (not served on the day of IMP administration), lunch, and dinner at about 0900, 1300, and 1900, respectively, each day. The same foods/beverages will be served to all subjects. When a scheduled test/blood collection conflicts with a meal, the subject will undergo the test/blood collection first.
- Eating will not be allowed between 10 hours before and 4 hours after IMP administration in each period.
- Fluid intake will not be allowed from 2 hours before to 2 hours after IMP administration in each period. Except for that period, subjects will be allowed to intake fluids freely.
- For each clinical laboratory test (excluding the tests scheduled the same day as IMP administration), eating will not be allowed from 2200 the day before to blood/urine collection.

Protocol 156-102-00136

4.2.4 Prohibition of the Supine Position

The subject will not be allowed to assume the supine position, excluding when it is necessary for an observation/test/examination, for at least 4 hours after IMP administration.

5 Reporting of Adverse Events

5.1 Definitions

An AE is defined as any untoward medical occurrence in a patient or clinical trial subject administered a medicinal product and which does not necessarily have a causal relationship with this treatment. AEs would not include information recorded as a symptom at screening for pre planned procedures for which the underlying condition was known and no worsening occurred. An adverse reaction is any untoward and unintended response to an IMP related to any dose administered.

A suspected adverse reaction is any AE for which there is a reasonable possibility that the IMP caused the AE.

An SAE includes any event that results in any of the following outcomes:

- Death
- Life-threatening; ie, the subject was, in the opinion of the investigator, at immediate risk of death from the event as it occurred. It does not include an event that, had it occurred in a more severe form, might have caused death.
- Persistent or significant incapacity/disability or substantial disruption of the ability to conduct normal life functions.
- Requires in-patient hospitalization or prolongs hospitalization.
 - Hospitalization itself should not be reported as an SAE; whenever possible the reason for the hospitalization should be reported.
 - Hospitalizations or prolonged hospitalizations for social admissions (ie, those required for reasons of convenience or other non-medical need) are not considered SAEs.
- Congenital anomaly/birth defect.
- Other medically significant events that, based upon appropriate medical judgment, may jeopardize the subject and may require medical or surgical intervention to prevent one of the outcomes listed above; eg, allergic bronchospasm requiring intensive treatment in an emergency room or home, blood dyscrasias or convulsions that do not result in hospitalization, or the development of drug dependency or drug abuse.

Protocol 156-102-00136

Nonserious adverse events are all AEs that do not meet the criteria for a “serious” AE.

Immediately Reportable Event (IRE):

- Any SAE.
- Any AE related to occupational exposure.
- Potential Drug Induced Liver Injury (DILI) case (see [Section 5.4](#)).
- Pregnancies in partners of male subjects are also defined as IREs. Although normal pregnancy is not an AE, it will mandate IMP discontinuation and must be reported on an IRE form to the sponsor. Pregnancy will only be documented on the AE CRF if there is an abnormality or symptom.

Clinical Laboratory Test Value Changes: It is the investigator’s responsibility to review the results of all laboratory tests as they become available. This review will be documented by the investigator’s dated signature on the laboratory report. For each abnormal laboratory test result, the investigator needs to ascertain if this is an abnormal (ie, clinically significant) change from baseline for that individual subject. This determination, however, does not necessarily need to be made the first time an abnormal value is observed. The investigator may repeat the laboratory test or request additional tests to verify the results of the original laboratory tests. If this laboratory value is considered medically relevant by the investigator (subject is symptomatic, requiring corrective treatment or further evaluation), or if the laboratory value leads to discontinuation, and/or fulfills a seriousness criterion, this is considered an AE.

Severity: Adverse events will be graded on a 3-point scale and reported as indicated on the CRF. The intensity of an adverse experience is defined as follows:

1 = Mild: Discomfort noticed, but no disruption to daily activity.

2 = Moderate: Discomfort sufficient to reduce or affect normal daily activity.

3 = Severe: Inability to work or perform normal daily activity.

IMP Causality: Assessment of causal relationship of an AE to the use of the IMP is defined as follows:

Related: There is a reasonable possibility of a temporal and causal relationship between the IMP and the AE.

Not Related: There is no temporal or causal relationship between the IMP and the AE.

Protocol 156-102-00136

5.2 Eliciting and Reporting Adverse Events

The investigator will periodically assess subjects for the occurrence of AEs. To avoid bias in eliciting AEs, subjects should be asked the non-leading question: "How have you felt since your last visit?" All AEs (serious and nonserious) reported by the subject must be recorded on the source documents and CRFs provided by the sponsor. Serious AE collection is to begin after a subject has signed the ICF and end at the time of discharge.

Use medical terminology in AE reporting. Adverse events should be reported as a single unifying diagnosis whenever possible or, in the absence of a unifying diagnosis, as individual signs or symptoms. Exacerbation or disease progression should be reported as an AE only if there are unusual or severe clinical features that were not present, or experienced earlier, or not expected based on the course of the condition.

A reported AE that undergoes a change in severity, seriousness, or toxicity should be reported as a new AE on the CRF.

In addition, the sponsor must be notified immediately by telephone, fax, or e-mail of any IREs according to the procedure outlined below, in [Section 5.3](#). Special attention should be paid to recording hospitalization and concomitant medications.

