6.5 Medical History

For the bioequivalence analysis set and safety analysis set, distributions for presence or absence of medical history and current symptoms will be calculated in each cohort, overall and for each group.

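### Protocol 5.2 keeps an ordinary, non-severe, expected post-dose worsening of a screening symptom off the AE form, although 5.1 makes it an AE

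*Protocol*

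**What the plan says.** Protocol 5.1 opens with a wide definition: "An AE is defined as any untoward medical occurrence in a patient or clinical trial subject administered a medicinal product". No causal link is needed, and neither severity nor expectedness limits it. One exclusion follows, for "information recorded as a symptom at screening for pre planned procedures for which the underlying condition was known and no worsening occurred".

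Protocol 5.2 governs what goes on the AE form. It contains three relevant rules:

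- A general duty: "All AEs (serious and nonserious) reported by the subject must be recorded on the source documents and CRFs provided by the sponsor".
- A restriction: "Exacerbation or disease progression should be reported as an AE only if there are unusual or severe clinical features that were not present", and the sentence continues "or experienced earlier, or not expected based on the course of the condition".
- A rule for events already on the form: "A reported AE that undergoes a change in severity, seriousness, or toxicity should be reported as a new AE on the CRF".

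Pre-existing symptoms are foreseen. Protocol 3.7.1.1 collects current symptoms among the screening demographics, and SAP 6.5 says that "distributions for presence or absence of medical history and current symptoms will be calculated".

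SAP 8.2 builds the TEAE tables from AEs that emerge after dosing in a period. It does not mention worsening of something already present. For safety measurements, Protocol 7.6 and SAP 8 take the value immediately before dosing in each period as baseline.

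**The concern.** The two sections set different thresholds for the same event. Under 5.1, a known symptom that gets worse after a dose is an untoward occurrence and so an AE. Under 5.2 it is reported only if its features pass a further test. The 5.2 sentence reads as though written for a trial in patients whose disease is expected to progress. No disease is under study here, so the sentence can act only on a subject's own minor pre-existing symptoms.

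The safety tables can count only what reaches the AE form. An event stopped at 5.2 is missing from the overall TEAE table, the severity table and the related-TEAE table, and no analysis step can restore it. The safety study summarised in Protocol 1.2.1 lists thirst and headache among its frequent events. Both are everyday complaints, and a worsening of either could look neither unusual nor severe.

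**Working it through.** The documents give no figure on this point, so the check compares the rules. Take a subject with a symptom known at screening, and ask of each kind of post-dose worsening whether it is an AE under 5.1 and whether any rule puts it on the AE form.

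| Case | AE under 5.1? | Reported? | By which rule |
|---|---|---|---|
| (a) Symptom held only as a screening current symptom; worsening ordinary, non-severe and expected | Yes | No | Stopped by the 5.2 exacerbation sentence |
| (b) Same symptom; worsening has unusual or unexpected features, even if mild or moderate | Yes | Yes | The same sentence lets it through |
| (c) Symptom already on the form as an AE, for example after consent or in an earlier period; severity changes | Yes | Yes, as a new AE | Change-in-severity rule, 5.2 |
| (d) New clinically significant physical finding, or medically relevant laboratory change | Yes | Yes | Protocol 3.7.2.3.1 and the laboratory paragraph of 5.1 |

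Only case (a) is lost. The next step is to see whether another rule recovers it:

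- The duty to record all AEs does not, because the exacerbation sentence decides what is reported as an AE.
- The change-in-severity rule does not, because it applies to an AE already reported. A mild headache logged as an AE that becomes moderate is a new AE. The same headache logged as a screening symptom is not, if the change is ordinary and expected.
- The physical-findings rule covers findings absent at baseline, and the laboratory rule covers test values. Neither covers a symptom that was present and got worse.
- SAP 8.2 works from AEs on the form, so it comes too late.

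The 5.1 exclusion is not needed for this result. Its wording is tied to pre-planned procedures, and taking it as a rule for every known condition would be an inference. The general definition in 5.1 already covers a worsening.

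Effect of one missed subject: Protocol 7.1 plans 42 subjects per cohort, each receiving all three treatments. One missed subject lowers overall TEAE incidence for a treatment by 1/42 = 2.4 percentage points, provided that all 42 receive it and that this subject has no other TEAE under it. A subject who also reports thirst, say, is already counted in the overall figure. Only the preferred-term, severity or related-event lines could then change.

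**The case against.** The strongest reply is that the 5.2 sentence has a wide exit. Unusual is an alternative to severe, and features not expected from the course of the condition also count. A headache made worse by the study drug is arguably not expected from that headache's own course, so an investigator could report it. This stands in part: it rules out saying that all mild or moderate worsening is lost. It does not close the gap. It makes reporting depend on the investigator first deciding that the worsening is not the condition's natural course, whereas the 5.1 definition asks for no causal judgement.

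A reader might also take the severe features of 5.2 to mean grade 3 on the 5.1 severity scale, so that every mild or moderate worsening would be unreported. The documents do not support this. They never link the phrase to the scale, which grades AEs already identified.

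The population is a fair further objection. Subjects are men aged 20 to 39, and clinically significant abnormalities or relevant history are excluded (Protocol 3.4.3). That leaves the sentence little to act on, though minor symptoms are not excluded and the plan provides for tabulating them. Pollakiuria is a weak example, since Protocol 1.3 reports it in patients with cirrhosis or ADPKD and 1.2.1 does not list it among the frequent events in healthy volunteers.

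**Conclusion.** The mismatch between 5.1 and 5.2 is real, and a stated rule causes it. It affects case (a) only. It bears on descriptive safety tables and leaves the AUCt and Cmax analyses and the bioequivalence decision untouched. This is a minor point, worth making because the correction is cheap.

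The number of subjects affected cannot be derived from the documents. A reader might infer that one or two subjects per treatment would be missed, by assuming that 2 to 4 of 42 have a current symptom and applying the AE rates of Protocol 1.2.1 at 15 and 30 mg: 2 × 2/6 = 0.7 and 4 × 5/12 = 1.7. That does not hold. The 2 to 4 has no source, and those rates are for any adverse event, not for worsening of one existing symptom. With the same assumed 2 to 4 subjects and the headache count in 1.2.1 (3 of 42 treated), the result is 2 × 3/42 = 0.14 to 4 × 3/42 = 0.29 subjects. That too is only an illustration, because new headache is not the same as worsening of an existing symptom. The true number is probably small and may be zero.

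The conclusion rests on a literal reading of 5.2 and on the symptom having been recorded only as a screening current symptom.

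**What to change.** Two matching changes are needed:

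- **Protocol 5.2.** Replace the exacerbation sentence with: any worsening after IMP administration of a pre-existing condition or symptom, compared with its state immediately before dosing in that period, is reported as an AE.
- **SAP 8.2.** Add that such worsening counts as a TEAE of the period in which it occurs.

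Use one comparator only. The predose state suits all three periods and matches the baseline that Protocol 7.6 and SAP 8 use for safety measurements. AEs are already assessed before dosing in each period (Protocol 3.7.1.4.1), so no new visit or procedure is needed. Changing 5.2 alone would leave it unclear whether a worsened symptom has emerged for the purposes of SAP 8.2.

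The cost is one sentence in each document and a few more mild AE records.

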6.8 Protocol Deviations

Distributions will be calculated for each type of significant deviation from the protocol in each cohort.

7 Efficacy Analysis

Not applicable.

8 Safety Analysis

Analysis will be performed by formulation and dosing regimen in each safety analysis set per cohort. Values obtained immediately before IMP administration in each period will be handled as baseline.

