8.2 Adverse Events

All adverse events (AEs) will be coded by system organ class (SOC) and preferred term (PT) (Medical Dictionary for Regulatory Activities [MedDRA] version 20.0). The incidence of the following events in subjects administered IMP using the relevant formulation and dosing regimen will be summarized for all events, by SOC, and by PT.

- Treatment-emergent AEs (TEAEs)
- TEAEs by severity
- TEAEs with an outcome of death
- Serious TEAEs

AEs that emerge after IMP administration in Periods 1 and 2 up to predose in the next period will be regarded as TEAEs in Periods 1 and 2, respectively. AEs that emerge after IMP administration in Period 3 will be regarded as TEAEs in Period 3. If there are multiple occurrences of the same event in the same period in the same subject, the event with the highest severity will be selected. The above summaries will also be prepared for TEAEs potentially causally related to the IMP.

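### An adverse event that is improving across a dose can be counted again as a TEAE of the next formulation or regimen, because SAP 8.2 does not require the event to be new or worse

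*Protocol*

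**What the plan says.** Protocol 5.1 sets three severity grades (mild, moderate, severe): "Adverse events will be graded on a 3-point scale and reported as indicated on the CRF". Protocol 5.2 then says: "A reported AE that undergoes a change in severity, seriousness, or toxicity should be reported as a new AE on the CRF". The only nearby limit concerns worsening: "Exacerbation or disease progression should be reported as an AE only if there are unusual or severe clinical features". Nothing there deals with improvement.

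SAP Section 8 sets the unit of the safety summary: "Analysis will be performed by formulation and dosing regimen in each safety analysis set per cohort". SAP 8.2 supplies the assignment rule for the first two periods, "AEs that emerge after IMP administration in Periods 1 and 2 up to predose in the next period will be regarded as TEAEs" of those periods, and for the last: "AEs that emerge after IMP administration in Period 3 will be regarded as TEAEs in Period 3". Its one rule for duplicates begins "If there are multiple occurrences of the same event in the same period in the same subject, the event with the highest severity", and that event is the one kept. The rule works within one period of one subject.

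Protocol 7.6.1 lists TEAEs among the summaries but does not define them. The period-specific baseline in Protocol 7.6 and SAP Section 8 concerns measured values, not adverse events.

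**The concern.** Taken together, the two rules can charge an event to a treatment that neither started it nor made it worse. The protocol turns a drop from moderate to mild into a new adverse event. If that drop falls after the next dose, the SAP has no rule that ties the new record to the episode already counted in the preceding period.

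In a crossover, the table of adverse events by formulation and regimen is useful only if each event sits in the right period. A re-counted event raises the incidence in the later column. It also makes the OD and conventional columns look more alike, because one episode stands in two of them, or in all three. The same records enter the severity tables, and enter the tables of IMP-related TEAEs when the new record is judged related.

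A pre-dose event has a similar route. Adverse events are collected from screening, so one that improves after the Day 1 dose could appear as a TEAE of the first treatment.

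**Working it through.** The plan states no figure on this point, so there is none to reproduce. The check applies the two rules to hypothetical episodes.

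Inputs:
- Doses on Days 1, 4 and 7 (Protocol Table 3.7-1), 72 hours apart (Protocol 3.2.2): hours 0, 72 and 144 from the Period 1 dose.
- Each grade change makes a new record (Protocol 5.2).
- A record belongs to the period in which it emerges, and the highest grade is kept within a period (SAP 8.2).
- Assumption: the new record's onset is the time of the grade change. Neither document gives an onset convention for such records.

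| Episode | Counted under the current text | Counted if only first onset or worsening counts |
|---|---|---|
| A. Moderate at 60 h, mild at 80 h, resolved at 100 h | Period 1 (moderate) and Period 2 (mild) | Period 1 |
| B. Moderate at 10 h, mild at 40 h, resolved at 80 h | Period 1 | Period 1 |
| C. Mild at 60 h, resolved at 80 h | Period 1 | Period 1 |
| D. Moderate at 60 h, mild at 150 h | Period 1 (moderate) and Period 3 (mild) | Period 1 |
| E. Severe at 60 h, moderate at 80 h, mild at 150 h | Periods 1, 2 and 3 | Period 1 |

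Episodes B and C mark the limits. A step-down before the next dose is absorbed by the within-period rule. An event that is mild throughout has no lower grade to step down to, and resolution is not a grade change. A second count therefore needs three things: a grade above mild at the time of a dose, a step-down after that dose, and a new record dated at the step-down.

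Size of one extra count: Protocol 7.1 plans 14 subjects per group, so 3 × 14 = 42 per cohort, and in a crossover all 42 contribute to each column if all are dosed.
- 42 dosed: 1/42 = 2.4 percentage points.
- 36 dosed (3 × 12, the required number before the dropout allowance): 1/36 = 2.8 percentage points.

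This is a maximum per row. SAP 8.2 summarises incidence in subjects, so the preferred-term row rises only if the subject has no other record of that term in the period. The all-events row does not move if the subject already has another TEAE there, and the system-organ-class row does not move if that other TEAE is in the same class.

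**The case against.** The strongest reply is that an event already present and improving does not naturally emerge after the next dose. On that reading, or if the new record kept the original onset date, there is no second count. The CRF, to which Protocol 5.1 refers for reporting severity, is not part of the documents. This reply stands in part: the double count is a consequence of a literal reading, not a stated instruction. But the protocol itself calls the record a new AE, and neither document says how to date it or how to treat an improving event. Two programmers could produce different tables from the same data.

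The second reply is that the conditions will rarely be met. Mean half-life at these doses is 3.33 to 4.39 hours (Protocol 3.7.3.1) against 72 hours between doses. In the earlier single-dose study, diuretic effects lasted to 24 hours in the 60 to 120 mg groups, above the doses used here (Protocol 1.2.1). Thirst, the commonest event in that study, should therefore settle within its own period. Eligibility is reassessed, with adverse events, on Days -1, 3 and 6 (Protocol 3.7.1.2 and 3.7.1.3), and a subject who needs a prohibited drug for an event leaves the trial (Protocol 4.1). All of this stands. It lowers the frequency but does not remove the gap, above all for intercurrent illness.

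A reader might go further and infer that the site is obliged to make the new record and that every resolving event is then re-counted. The documents do not support this: Protocol 5.2 uses *should*, and episodes B and C are counted once. A reader might also use the four subjects with nasopharyngitis in the earlier study to predict some number of spurious TEAEs per cohort. Protocol 1.2.1 gives neither durations nor grades for those cases and pools them over 15 to 120 mg, so no such number can be derived. Nor does an extra count always reach the IMP-related tables; that depends on the causality judgement for the new record.

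**Conclusion.** The point holds as a gap in the TEAE definition. Protocol 5.2 makes a new event of any severity change, and SAP 8.2 assigns events by emergence, with no link across periods and no requirement that the event be new or worse. Under the stated onset assumption, an event above mild that crosses a dose and then steps down is counted again under the next formulation or regimen. The size is at most 2.4 percentage points per case in a row of that column with 42 dosed. The number of cases cannot be estimated from the documents and is probably small.

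A reader might infer that the trial's main conclusion is at risk. It is not: the objective and primary variables concern AUCt and Cmax, and the adverse event tables are descriptive, with no test or decision rule attached. The point is worth settling because the rules as written can attribute an event to the wrong treatment, and one clarification removes the ambiguity.

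**What to change.** In SAP 8.2, define a TEAE of a period as an adverse event with first onset, or with an increase in severity or seriousness, after that period's dose and before the next dose (for Period 3, after the Period 3 dose). Add that a record documenting only a lower severity of an ongoing event keeps the original onset and period and is not a new TEAE. Real worsening after a later dose would still be counted in that later period.

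The cost is some programming or data review to match continuation records by subject, term and dates. No new CRF field is required. Protocol 5.2 can stay as it is; limiting its rule to worsening would be an optional tidying, since the SAP definition alone resolves the counting.
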